2.4 Potential Risks and Benefits

2.4.1 Potential Risks

Potential risks of study procedures (venipuncture, inguinal LN biopsy, and colonoscopy with GALT biopsies) are detailed in Section 7.1 and in consent forms. According to the Losartan package insert, the most severe risks of losartan use include teratogenicity in the setting of pregnancy, hypersensitivity, symptomatic hypotension, worsening of renal function, and electrolyte abnormalities. The most common side effects of losartan include fatigue, weakness, diarrhea, chest pain, tachycardia and anemia.

Subjects will be rigorously screened to ensure that they are at low risk for complications due to losartan and they will be monitored closely for side effects and signs of toxicity. The most common side effects of Gardasil include headache, fever, nausea, dizziness and injection site reactions. Severe reactions, including hypersensitivity, are rare. The most common side effects of Stribild are new onset or worsening of renal impairment, bone effects, fat distribution and immune reconstitution syndrome. The most common side effects of Stribild include nausea, diarrhea, abnormal dreams, headache, rash, fatigue, dizziness, insomnia, flatulence, somnolence, ocular icterus and jaundice. The most common side effects of Prezista are drug –induced hepatitis, skin reactions ranging from mild to severe, use with caution with a known sulfonamide allergy, new onset diabetes or hyperglycemia, redistribution/accumulation of body fat or immune reconstitution syndrome and subjects with hemophilia may develop increased bleeding events, The most common side effects of Prezista include diarrhea, nausea, rash, headache, abdominal pain and vomiting.

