5. Prior diagnosis of a chronic inflammatory disease with serologic or clinical evidence as diagnosed by a primary care physician or specialist. Examples of these include, but are not limited to, systemic lupus erythematosus, rheumatoid arthritis, scleroderma, Sjogren's syndrome, mixed connective tissue disease, psoriasis, polymyositis, dermatomyositis, vasculitis, sarcoidosis, Wegener's granulomatosis, giant cell arteritis, polyarteritis nodosa, gastrointestinal pemphigoid, eosinophilic colitis, Crohn's disease, ulcerative colitis, autoimmune hepatitis.
6. Prior diagnosis of a connective tissue disease with genetic, serologic or clinical evidence as diagnosed by a primary care physician or specialist. (Marfan's syndrome, Ehlers-Danlos syndrome).
7. Screening systolic blood pressure < 110.
8. Estimated Glomerular Filtration Rate (eGFR) of < 30ml/min/1.73 m² within 60 days of study initiation or history of advanced renal disease.
9. AST and/or ALT > 3 times the upper limit of normal within 60 days of study enrollment.
10. Potassium > 5.0 within 60 days of study enrollment.
11. Pregnancy.
12. In women of childbearing age, unwillingness to use birth control for the duration of the study.
13. Breast feeding.
14. Prior vaccination with an HPV vaccine, including Cervarix (GlaxoSmithKline) or Gardasil (Merck).
15. History of hypersensitivity or severe allergic reactions to yeast.
16. At the principle investigator's discretion if not a suitable surgical candidate.
17. Currently undergoing treatment for hepatitis C or treatment completed within the last 3 months
18. History of ≥ 3 previous inguinal lymph node biopsies

HIV-uninfected:

a. Inclusion Criteria

Participants must meet all of the following inclusion criteria to participate in this study:

1. HIV uninfected.
2. ≥ 18 years of age.
3. No contraindication to proposed study procedures.

b. Exclusion Criteria

Participants meeting any of the following exclusion criteria at baseline will be excluded from study participation:

1. Use of any immunomodulator within the 12 months prior to study enrollment (as defined above).
2. Current use of an ARB or ACEi.
3. Prior diagnosis of a chronic inflammatory disease with serologic or clinical evidence (as defined above).
4. Prior diagnosis of a connective tissue disease with genetic, serologic or clinical evidence as diagnosed by a primary care physician or specialist. (Marfan's syndrome, Ehlers-Danlos syndrome).

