5. AST and/or ALT > 1.5 times the upper limit of normal at screen
6. At the principal investigator's discretion if not a suitable candidate.
7. Sulfa allergy
8. Pregnancy.

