6.4 Prohibited Medications

The following drugs are not permitted for HIV subjects while on study:

- Any immunomodulator (defined as a drug known to either diminish or augment a patient's immune system). Examples include, but are not limited to, systemic corticosteroids (use of topical steroids will be permitted), TNF-inhibitors, rituximab, cyclophosphamide, abatacept, cyclosporine, azathioprine, 6-mercaptopurine, methotrexate, sulfasalazine, cyclosporine, tacrolimus, sirolimus, and intravenous immune globulin.
- ACE inhibitors
- ARBs other than the study drug
- Rifampin
- Lithium
- Fluconazole

The following drugs are not permitted for uninfected control subjects while taking Stribild and Prezista:

- Any antiretroviral drugs

- Any nephrotoxic drugs
- Any drugs that are highly dependent on CYP3A for clearance and for which elevated plasma concentrations are associated with serious and/or life-threatening events

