8.4.1 Screening

At this visit, consents will be reviewed in detail and the subject will have the opportunity to ask any questions they may have. The designated study staff or physician will interview the participant and a physical exam will be performed. Blood will be obtained for HIV antibody, liver function tests, electrolyte panel including creatinine, and CBC. Screening for hepatitis C will also be performed. Women of childbearing age will have a urine pregnancy test. Once lab results are available (within 3 days), they will be reviewed by designated study staff to ensure that laboratory inclusion/exclusion criteria are met. If the subject has met all entry criteria, they will be contacted by the designated study staff. The study protocol will again be reviewed and if the subject is still interested in enrolling, they will be scheduled for the study visit. Subjects who have not met the criteria will also be contacted by the designated study staff and told that they do not qualify to participate in the study

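### The five HIV-uninfected volunteers given Stribild and Prezista have no renal-function exclusion, although creatinine is drawn at screening, and no maximum age for screening labs at first dose

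*Combined protocol and SAP*

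**What the plan says.** Section 5.2 has a single eligibility list for all HIV-uninfected subjects. It covers the biopsy-only controls and the five additional controls who, under sections 2.2 and 8.4.3, take Stribild and Prezista for two weeks. Of its eight exclusions, one is a chemistry limit: "AST and/or ALT > 1.5 times the upper limit of normal at screen". None mentions creatinine, eGFR or renal history.

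For screening of the five, section 8.4.1 states: "Blood will be obtained for HIV antibody, liver function tests, electrolyte panel including creatinine, and CBC". Once results are back, "they will be reviewed by designated study staff to ensure that laboratory inclusion/exclusion criteria are met". Section 8.4.3 then brings volunteers back to collect the drugs. It gives no maximum interval since screening and no repeat laboratory check. Table 2 (section 8.5) marks only adherence counselling at drug pick-up.

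Elsewhere the protocol recognises the renal risk. Section 2.4.1 says: "The most common side effects of Stribild are new onset or worsening of renal impairment". Section 6.4 lists among the drugs barred while these controls are dosed: "Any nephrotoxic drugs".

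The HIV-infected list does have a renal exclusion: an eGFR below 30 mL/min/1.73 m² "within 60 days of study initiation or history of advanced renal disease". Section 8.1.1 limits those subjects' screening labs to 60 days at randomization and requires a new chemistry panel beyond that. Section 8.1.2 adds an eligibility sign-off on the day of randomization.

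**The concern.** The screening step compares laboratory results with written criteria. For creatinine in this group there is nothing to compare with, so a volunteer with reduced renal function passes every stated laboratory criterion. The volunteer then receives a product whose renal effect the protocol itself names. Likewise, an AST/ALT result read at screening stays valid for any length of time before the first dose.

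Section 2.4.2 offers controls no direct benefit, so the entry rules carry much of their protection. What is at stake is the safety of five people. The randomized comparison, its power and its error rates are unaffected.

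**Working it through.** The plan states no figure to reproduce here. The check sets the entry rules for the two dosed groups side by side.

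| Item | HIV-infected (losartan or placebo) | Five dosed controls |
|---|---|---|
| Renal exclusion (5.2) | eGFR < 30 mL/min/1.73 m², or history of advanced renal disease | none |
| AST/ALT limit (5.2) | > 3 × ULN, within 60 days | > 1.5 × ULN, at screen |
| Creatinine at screening | yes (8.1.1) | yes (8.4.1) |
| Maximum lab age at start of drug | 60 days, else chemistry redrawn (8.1.1) | none stated (8.4) |
| Eligibility sign-off on the day of starting | yes (8.1.2) | none stated (8.4.3) |

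1. *Is the uninfected list simply looser throughout?* No. Its AST/ALT limit is half the infected one (1.5 / 3 = 0.5), and it adds a sulfa-allergy exclusion, which matches a Prezista caution in section 2.4.1. The list was adapted to the dosed controls for liver function and allergy but not for renal function.

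2. *Does another rule supply a renal limit?* The section 6.4 ban concerns concomitant drugs, not the volunteer's own renal function. The section 9.7.2 removal criteria for healthy controls name rash, gastrointestinal symptoms and clinical hepatitis, and nothing renal. The count of renal thresholds for these five is 0 at entry and 0 for removal.

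3. *Does another rule date the labs?* The exclusion header reads: "Participants meeting any of the following exclusion criteria at baseline will be excluded from study participation". Taken in its ordinary sense, that means at entry. It does not say how old a result may be at that time, and Table 2 has no baseline visit to tie it to. In section 8.4 the word baseline is used only for the pharmacokinetic draw at week 2, after dosing.

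4. *When would a 60-day rule act?* The documents give no usual interval from screening to first dose. If it is 1 to 8 weeks (assumed), that is 7 to 56 days, within the 60-day limit, and no redraw is triggered. At 9 weeks (63 days) it would be. The rule is a backstop against delay.

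**The case against.** The strongest reply is that judgement already covers this. The protocol summary requires uninfected subjects to be healthy. Control inclusion 3 requires "No contraindication to proposed study procedures". Control exclusion 6 lets the investigator refuse anyone not a suitable candidate, which is broader than the surgical wording on the infected list. Section 6.3 obliges investigators to review the current package insert whenever a study agent is started. The investigator therefore has both the creatinine value and the label to hand, and the label is also where the proposed cut-off would come from. This stands as mitigation: harm would require several safeguards to fail together. It does not close the gap, because none of these gives the staff who clear the results a renal value to apply or a date after which results lapse.

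It is also fair that the eGFR limit of 30 was set for subjects starting losartan, and nothing in the documents ties it to Stribild or Prezista. It can serve only as a floor.

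Two stronger readings are tempting, and the documents do not support either.

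- A reader might infer that about 14 daily doses before the next chemistry marked in Table 2 is a monitoring shortfall. Infected subjects starting losartan, for which section 2.4.1 also names worsening renal function, have their first toxicity labs at day 14 too (section 8.1.3). The on-drug interval is the same.
- A reader might infer that Table 2 omits a baseline pregnancy test promised in sections 7.2 and 9.5. Those sections pair that test with three-monthly testing, and 9.5 refers to stopping losartan or Gardasil, so they describe the 30-month schedule. For these five, note 2 of Table 2 governs and requires a negative test before enrolment.

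**Conclusion.** The point holds as a low-severity participant-safety gap for five volunteers. As written, the entry rules contain no renal limit for people given a product with a named renal risk, and no expiry for their screening labs. The missing renal limit is the more important half because it applies however soon dosing follows screening. The lab-age half matters only if the first dose falls more than 60 days after screening, and nothing in the documents shows that such delays are expected.

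The conclusion rests on the text of sections 5.2, 8.4 and 8.5. The documents give no rate of renal events and no distribution of renal function among volunteers, so no probability of harm can be derived. They do not support a claim that anyone unsuitable would in fact be dosed, since investigator discretion and the insert review may well prevent it.

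**What to change.** For the five dosed controls only:

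1. Add to section 5.2 a renal exclusion read from the screening creatinine. It should be no looser than the infected-list rule (eGFR < 30 mL/min/1.73 m² or a history of advanced renal disease). The sponsor should take the final value from the Stribild and Prezista labels. It is likely to be stricter than 30, given that these are meant to be healthy volunteers.
2. Add to section 8.4 the 60-day limit and chemistry redraw of section 8.1.1, counted to the first dose. Routine chemistry at drug pick-up is not needed when screening labs are within 60 days.

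The cost is amendment wording. The first change needs no extra blood draw. The second needs one only for a volunteer more than 60 days past screening, whose first dose would wait for the result (within 3 days, at the turnaround in section 8.4.1). One or two more screen failures are possible; that figure is an assumption.

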5.3 Co-Enrollment Guidelines

Subjects are restricted from taking part in any other studies that involve tissue sampling or administration of pharmacologic agents while enrolled in this protocol.

6. STUDY AGENTS

6.1 Study Agent Acquisition

6.1.1 Losartan

6.1.1.1 Formulation, Packaging, and Labeling

Losartan will be provided for this study by Merck and will be shipped directly to the Investigational Drug Services (IDS) pharmacy at the University of Minnesota. Matched placebo pills will also be provided by Merck. IDS pharmacy will maintain randomization codes and will provide appropriate labels for medications distributed to subjects.

6.1.1.2 Preparation, Administration, Storage, and Dosage of Study Agent(s)/Intervention(s)

HIV infected subjects will be randomized to placebo or losartan. Starting dose of losartan will be 50 mg po daily. At week 2, dose will be increased to 100 mg po daily based on tolerability, blood pressure, and toxicity lab results. The IDS pharmacy will be responsible for preparing pill bottles, distributing medications to subjects, and storing medications. Research pharmacists and credentialed pharmacy technicians charged with dispensing research-related drugs will receive protocol-specific training and are compliant with State Board of Pharmacy requirements, FDA guidelines, and Good Clinical Practices.

6.1.1.3 Study Agent Accountability Procedures

Losartan or placebo will be distributed to subjects at baseline visit, week 2 visit and approximately every 3 months thereafter. Pharmacy documents, including study drug accountability logs, study drug ordering/shipping logs, and regulatory documents are maintained by the pharmacy technician. All handling of study agents (e.g., drug receipt and storage, drug

accountability, etc.) will be done by a pharmacist. If subjects have study drug remaining at time of study completion or study withdrawal, designated study staff will collect the drug from the subject and return it to the UMN IDS where it will be properly disposed of.

6.1.2 Gardasil Vaccine

6.1.2.1 Formulation, Packaging, and Labeling

Standard pre-filled syringes of Gardasil will be purchased commercially through Merck for use in this study and will be shipped directly to the IDS pharmacy.

6.1.2.2 Preparation, Administration, Storage, and Dosage of Study Agent(s)/Intervention(s)

Gardasil will be stored in the IDS pharmacy and will be distributed by the pharmacy to designated study staff on the day of vaccine visits. Research pharmacists and credentialed pharmacy technicians charged with dispensing research-related drugs will receive protocol-specific training and are compliant with State Board of Pharmacy requirements, FDA guidelines, and Good Clinical Practices. Trained study staff will administer 0.5mL of Gardasil (which contains suspension of 120 mcg L1 protein from HPV types 6, 11, 16, and 18) intramuscularly in the thigh of HIV infected subjects at months 23, 25 and 29.5.

6.1.2.3 Study Agent Accountability Procedures

Pharmacy documents, including study drug accountability logs, study drug ordering/shipping logs, and regulatory documents are maintained by the pharmacy technician. All handling of study agents (e.g., drug receipt and storage, drug accountability, etc.) will be done by a pharmacist. IDS will properly dispose of any product that remains when the study is completed.

6.1.3 Stribild

6.1.3.1 Formulation, Packaging, and Labeling

STRIBILD is a fixed-dose combination tablet containing elvitegravir, cobicistat, emtricitabine, and tenofovir DF for oral administration. Stribild will be provided for this study by the research study and will be shipped directly to the Investigational Drug Services (IDS) pharmacy at the University of Minnesota.

6.1.3.2 Preparation, Administration, Storage, and Dosage of Study Agent(s)/Intervention(s)

HIV non-infected subjects will receive **150 mg elvitegravir/150 mg cobicistat/200 mg emtricitabine/300 mg tenofovir disoproxil fumarate to take by mouth once daily**. The IDS pharmacy will be responsible for preparing pill bottles, distributing medications to subjects, and storing medications. Research pharmacists and credentialed pharmacy technicians charged with dispensing research-related drugs will receive protocol-specific training and are compliant with State Board of Pharmacy requirements, FDA guidelines, and Good Clinical Practices

6.1.3.3 Study Agent Accountability Procedures

Pharmacy documents, including study drug accountability logs, study drug ordering/shipping logs, and regulatory documents are maintained by the pharmacy technician. All handling of study agents (e.g., drug receipt and storage, drug accountability, etc.) will be done by a pharmacist. If subjects have study drug remaining at time of study completion or study withdrawal, designated study staff will collect the drug from the subject and return it to the UMN IDS where it will be properly disposed of.

6.1.4 Prezista

6.1.4.1 Formulation, Packaging and Labeling

Prezista comes in tablets or oral suspension. Prezista will be provided for this study by the research study and will be shipped directly to the Investigational Drug Services (IDS) pharmacy at the University of Minnesota.

6.1.4.2 Preparation, Administration, Storage and Dosage of Study Agent(s)/Intervention(s). HIV non-infected subjects will receive 800 mg of Prezista to take by mouth once daily. The IDS pharmacy will be responsible for preparing pill bottles, distributing medications to subjects, and storing medications. Research pharmacists and credentialed pharmacy technicians charged with dispensing research-related drugs will receive protocol-specific training and are compliant with State Board of Pharmacy requirements, FDA guidelines, and Good Clinical Practices.

6.1.4.3 Study Agent Accountability Procedures

Pharmacy documents, including study drug accountability logs, study drug ordering/shipping logs, and regulatory documents are maintained by the pharmacy technician. All handling of study agents (e.g., drug receipt and storage, drug accountability, etc.) will be done by a pharmacist. If subjects have study drug remaining at time of study completion or study withdrawal, designated study staff will collect the drug from the subject and return it to the UMN IDS where it will be properly disposed of.

6.2 Assessment of Participant Adherence with Study Product

Adherence to study drug (losartan or placebo) will be assessed by designated study staff at each study visit (these occur at least quarterly throughout the 30-month study). Subjects will be asked to bring their pill bottle to each of these visits so that remaining pills can be counted and used as a measure of adherence. Gardasil will be administered at appropriate dosing intervals by designated study staff, ensuring proper adherence.

6.3 Permitted Medications and Procedures

Medications not listed under prohibited medications and the manufacturers' package inserts are permitted during this study. If subjects develop a condition that requires a medical procedure while on study, we will determine impact of this on study participation on a case by case basis. Whenever a concomitant medication or study agent is initiated or a dose is changed, investigators must review the concomitant medications and study agents' most recent package inserts, and Investigator's Brochures to obtain the most current information on drug interactions, contraindications, and precautions.

6.4 Prohibited Medications

The following drugs are not permitted for HIV subjects while on study:

- Any immunomodulator (defined as a drug known to either diminish or augment a patient's immune system). Examples include, but are not limited to, systemic corticosteroids (use of topical steroids will be permitted), TNF-inhibitors, rituximab, cyclophosphamide, abatacept, cyclosporine, azathioprine, 6-mercaptopurine, methotrexate, sulfasalazine, cyclosporine, tacrolimus, sirolimus, and intravenous immune globulin.
- ACE inhibitors
- ARBs other than the study drug
- Rifampin
- Lithium
- Fluconazole

The following drugs are not permitted for uninfected control subjects while taking Stribild and Prezista:

- Any antiretroviral drugs

- Any nephrotoxic drugs
- Any drugs that are highly dependent on CYP3A for clearance and for which elevated plasma concentrations are associated with serious and/or life-threatening events

7. STUDY PROCEDURES/INTERVENTIONS

7.1 Description and Potential Risks of Clinical Procedures

7.1.1 Medical History

At screening and baseline visits, an extensive medical history will be obtained (including prior diagnoses, medications, surgeries, etc.). Interval medical histories will be obtained at each subsequent study visit. Only trained designated study staff or physicians will obtain the medical history. History will primarily be obtained by interviewing the subject. If the subject is agreeable and signs a release of information form, medical records may also be obtained and reviewed by the study clinical team. Obtaining a medical history may make subjects feel uncomfortable or embarrassed. There are no other potential risks.

7.1.2 Physical Exam

At screening, a physical exam will be performed which will include measurement of vital signs and evaluation of heart, lungs, abdomen, and neurologic and lymphatic systems. At all other time points indicated, a targeted physical examination including measurement of vital signs and evaluation of heart, lungs, abdomen, prior LN biopsy sites, and neurologic system will be performed. Only trained study staff and study physicians will perform exams. Performing a physical exam may make subjects feel uncomfortable or embarrassed. There are no other potential risks.

